## 4. STATISTICAL METHODS

### 4.1. Sample Size Justification

Approximately 70 patients will be randomized in Part I and approximately 440 patients will be randomized in Part II in this study (an estimated 35 and 220 per treatment group, respectively.)

For Part I, a sample size of approximately 35 per arm will provide information regarding the treatment effect. For Part II of the study, the expected sample size was determined based on the primary endpoint as follows. A minimum sample size of N=212 per arm for the placebo and the FX006 group has 90% power to yield a statistically significant difference (alpha=0.05, 2-sided) if the true underlying difference at Week 12 is 0.65 and with an assumption of 2.0 for the standard deviation (SD). For the first key secondary endpoint, the sample size of N=220 per treatment group has 90% power to yield a statistically significant difference between FX006 and placebo if the true underlying difference is 0.68 at Week 12, assuming a SD of 2.125. An early discontinuation rate of 6% was assumed. The data from Part I may be used to inform if the above assumptions were appropriate and the planned sample size for Part II should remain at 440, or whether a smaller sample size would be feasible.

### 4.2. General Statistical Methods and Data Handling

#### 4.2.1. General Methods

All outputs will be incorporated into Portable Document Format (PDF) or Word files, sorted and labeled according to the International Conference on Harmonization (ICH) recommendations, and formatted to the appropriate page size(s).

Tables will be presented as described in the sections below. Summary data will be presented by treatment group. For patient disposition, protocol deviations, demographic and baseline characteristics, OA medical history and study drug exposure, a total group that includes both treatment groups will also be presented. Any exceptions to this are described in the appropriate sections below.

For categorical variables, summary tabulations of the number and percentage within each category (with a category for missing data) of the parameter will be presented.

For continuous variables, the number of non-missing values (n), the mean, median, SD, minimum and maximum values will be presented. 95% confidence intervals (CI) may be provided. Additional statistics may be presented for certain endpoints as described below.

All collected data will be presented in by-patient listings sorted by treatment arm and patient number.

All data listings that contain an evaluation date will contain a relative study day (Rel Day Dose 1). Pre-treatment and post-treatment study days are numbered relative to the day of the first dose of study treatment, which is designated as Day 1. The preceding day is Day -1, the day before that is Day -2, etc.

The sections below describe the intended analysis of the endpoints. Additional sensitivity analyses may be employed in the event of any unforeseen data anomalies or data issues not known at the time of writing this analysis plan.

#### **4.2.2. Computing Environment**

All descriptive statistical analyses will be performed using SAS® statistical software (Version 9.4 or higher), unless otherwise noted.

AEs will be coding using Medical Dictionary for Regulatory Activities (MedDRA) Version 21.1 (or higher).

Concomitant medications will be coded using World Health Organization (WHO) Drug Dictionary (DD) (Version Mar 2014 or Higher).

#### **4.2.3. Methods of Pooling Data**

Not applicable to the present study.

#### **4.2.4. Adjustments for Covariates**

The primary endpoint and secondary endpoints will be analyzed with a longitudinal mixed model for repeated measures (MMRM) with fixed effects for treatment group, study week, treatment-by-week interaction, Baseline score of the endpoint, Baseline WOMAC A score and study site. All models will include Baseline WOMAC A score as a covariate, regardless of the endpoint, since randomization was stratified by WOMAC A scores.

AUE will be calculated and comparisons of the AUE endpoints will be estimated from an Analysis of Covariance (ANCOVA) with model parameters for treatment group and covariates of Baseline score of the AUE endpoint, WOMAC A score and study site. All models will include Baseline WOMAC A score as a covariate, regardless of the AUE endpoint, since randomization was stratified by WOMAC A scores.

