### 2.4.2. Key Secondary Efficacy Endpoints

- Change from Baseline on the WOMAC C (function) score at Week 12
- Patients' Global Impression of Change (PGIC) score at Week 12

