#### **4.2.10. Baseline definitions**

Baseline is the Baseline/Day 1 assessment prior to administration of the first dose of study treatment. If the Baseline result is missing, the last non-missing result prior to administration of study treatment may be used from the screening period.

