#### 4.10.1.1. Change from Baseline

For the WOMAC subscales, scores at each assessment time point (Baseline, Week 1, Week 4, Week 8, Week 12, etc.) will be calculated as the average of the responses to all questions in the subscale. Total score will be computed as the average of the average responses on each of the subscales (e.g. Average A + Average B + Average C divided by 3). This will provide a uniform scoring of 0 to 10 for each subscale and easier interpretation. Imputation rules are as presented in [Section 4.2.8](#).

Each of the WOMAC subscales will be analyzed separately using a longitudinal MMRM with fixed effects for Baseline score for the endpoint, treatment group, study week, treatment-by-week interaction, study site, and Baseline WOMAC A score. The analysis will include all study weeks of data, and not be confined to only that at Baseline and Week 12. Subject will be the random effect. Treatment differences from placebo will be estimated via least squares (LS) means from the analysis model along with 95% CIs, and associated 2-sided p-values. This model assumes missing at random and includes only observed data.

This model will be run using the SAS/STAT PROC MIXED procedure with an unstructured correlation matrix to model the within-subject errors. If the unstructured covariance matrix does not converge when fitting the mixed model, further investigation into the most appropriate correlation matrix will be conducted. The final selection of the correlation matrix to be used in fitting the mixed model will be presented in the table output and fully documented in the results section of the CSR.

Sample SAS code that can be used to implement the mixed analysis is provided below:

```
proc mixed data= dsin1 method=reml;
  class subjid armcd avisitn site;
  model chg = base armcd avisitn armcd*avisitn site base_womaca;
  repeated avisitn /type=un subject=subjid;
  lsmeans armcd/diff=control ('0') cl;
  /*[where 0 represents treatment=placebo]*/
  lsmeans armcd*avisitn /pdiff cl;
run;
```

Descriptive statistics will also be presented and will include number of observations, unadjusted mean, SD, median, minimum and maximum. Change from Baseline will also be presented. For the change from Baseline calculation, Baseline is the WOMAC result obtained on Day 1 prior to first dose. The adjusted change from Baseline will also be presented using results from the MMRM.

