#### 4.10.2. PGIC Score

##### 4.10.2.1. Continuous

The continuous PGIC score will be analyzed similar the WOMAC A (pain) analysis described in [Section 4.10.1.1](#). All available study visits will be analyzed and presented.

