##### 4.10.2.2. Categorical

In addition, the PGIC scores will be collapsed and categorized as follows:

PGIC Score	Category
1 = Very Much Improved	A = Improved
2 = Much Improved	A = Improved
3 = Minimally Improved	B = Minimal – No Change
4 = No Change	B = Minimal – No Change
5 = Minimally Worse	B = Minimal – No Change
6 = Much Worse	C = Worse
7 = Very Much Worse	C = Worse

The percent of "Improved" subjects (among those patients with available data) at each study visit will be compared between the FX006 treatment group and the placebo group using logistic regression, displaying the p-value and OR (with CI) for each comparison. Baseline score of the endpoint, Baseline WOMAC score and study site will be covariates in each model. Bar charts by visit and treatment will be presented for the collapsed categories of "Improved", "Minimal – No Change", and "Worse".

---

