#### 4.10.3. OMERACT-OARSI and Responder Status

The OMERACT-OARSI responder criteria will also be used to define response (Pham, 2004) using a combination of pain, function, and a patient assessment to form a composite endpoint. The WOMAC A pain subscale, WOMAC C function subscale, and PGIC will be used to derive the composite responder variable. While the OMERACT-OARSI defines patient assessment in terms of numeric changes from Baseline, this study only collects the PGIC which is a static assessment collected at post-Baseline visits asking how the patient feels relative to Baseline; thus, the responder criteria is being modified slightly for this context to consider PGIC responders as those reporting "Very Much Improved" or "Much Improved" status. Patients will be considered responders at a given weekly assessment if they show:

- At least a 50% improvement from Baseline in the WOMAC A pain subscale and an absolute improvement of at least 20 points or at least a 50% improvement from Baseline in the WOMAC C function subscale and an absolute improvement of at least 20 points; OR
- At least two of the following:

- 
- At least a 20% improvement from Baseline in the WOMAC A pain subscale and an absolute improvement of at least 10 points
  - At least a 20% improvement from Baseline in the WOMAC C function subscale and an absolute improvement of at least 10 points
  - PGIC of "Very Much Improved" or "Much Improved"

It should be noted for the WOMAC Index that higher scores indicate worse function. Also, the absolute change in the responder criteria assumes the WOMAC is on a 100 point scale. To normalize the WOMAC A pain score, the sum of the 5 pain questions will be multiplied by 2. To normalize the WOMAC C function score, the sum of the 17 function questions will be multiplied by 0.59. Imputation of WOMAC A and C scores will follow the rules as displayed in [Section 4.2.8](#). If WOMAC A or C scores cannot be imputed due to the amount of missing data or patients are missing PGIC at a given week, those patients will be counted as missing/not evaluable in the tabulations.

The OMERACT analysis will be conducted in the same way as the WOMAC A (pain) Responder analysis as described in [Section 4.10.1.3](#). All available study visits will be analyzed and presented.

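### The PGIC models require a Baseline PGIC score that is never collected, and the SAP waives that covariate for TSQM-9 but not for PGIC

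*SAP*

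**What the plan says.** SAP Section 2.4.2 lists "Global Impression of Change (PGIC) score at Week 12" as a key secondary endpoint. Three places then determine how PGIC is modelled.

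- Section 4.2.4 gives the general rule for primary and secondary endpoints, an MMRM "with fixed effects for treatment group, study week, treatment-by-week interaction, Baseline score of the endpoint, Baseline WOMAC A score and study site". It makes no exception for PGIC.
- Section 4.10.2.1 reads "The continuous PGIC score will be analyzed similar the WOMAC A (pain) analysis described in" Section 4.10.1.1. The model there is a "longitudinal MMRM with fixed effects for Baseline score for the endpoint, treatment group, study week" and further terms, and its sample code is "model chg = base armcd avisitn armcd*avisitn site base_womaca".
- Section 4.10.2.2, on the categorical PGIC analysis by logistic regression, states: "Baseline score of the endpoint, Baseline WOMAC score and study site will be covariates in each model".

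On collection, the schedules (SAP Table 1, protocol Table 7-2) show PGIC at Weeks 1, 4, 8 and 12 of the double-blind phase, with no entry at Screening 1, Screening 2 or Day 1. The questionnaire sequence in protocol Table 7-6 agrees. SAP Section 4.10.3 says that "this study only collects the PGIC which is a static assessment collected at post-Baseline visits".

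Section 4.10.8 faces the same situation for TSQM-9 and removes the Baseline score from that model because the questionnaire was not given at Baseline.

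**The concern.** A covariate that is missing for every patient cannot enter a model, yet the SAP puts one into both PGIC analyses. PGIC at Week 12 is one of only two key secondary endpoints. If the text is followed, its LS means, odds ratios, confidence intervals and p-values do not exist. If it is not followed, the analyst departs from the SAP without a written rule, in an analysis that Section 4.4 says is done unblinded. Section 5, which lists the changes from the protocol, mentions logistic regression for categorical PGIC as a way to adjust for covariates, but records no exception for the missing Baseline score.

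**Working it through.** The plan gives no figure to reproduce here. The check compares the terms that the models need with the data that the schedule supplies.

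1. **Term required.** The endpoint's Baseline score is named in 4.2.4, in the model text of 4.10.1.1 that 4.10.2.1 refers to, and in 4.10.2.2.
2. **Data available.** PGIC is recorded at Weeks 1, 4, 8 and 12 only, so the number of patients with a Baseline PGIC value is 0.
3. **Fallback.** Section 4.2.10 says: "If the Baseline result is missing, the last non-missing result prior to administration of study treatment may be used from the screening period". PGIC is not given at screening either, so this supplies nothing. Section 4.2.8 rules out imputation, apart from item-level scoring rules for WOMAC and HOOS-QOL.
4. **Constant Baseline.** Setting every Baseline to 4 (no change) does not help. The column is then a multiple of the intercept, and the two columns together have rank 1 of 2.
5. **Usable records.** With about 70 patients and four visits there are at most 70 × 4 = 280 double-blind PGIC records. This is an upper bound, because it assumes no dropout and counts the six incompletely dosed patients, whom the SAP excludes from the FAS. In a simulated data set of that layout, 0 of 280 records were complete with the Baseline term and 280 of 280 without it. A simplified mixed model (random intercept per subject) then converged. The zero follows by definition; the simulation only illustrates it.
6. **Response.** The sample code in 4.10.1.1 uses `chg`. For PGIC that would also be missing for everyone, so deleting `base` while keeping `chg` would still leave 0 records. The response must be the observed score.

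Outputs affected, counted from SAP Section 7.1 over the four double-blind visits:

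- Continuous PGIC tables: 14.2.2.1, 14.2.2.1.1.1 to .3, 14.2.2.1.2.1 to .2 = 6.
- Categorical PGIC tables: 14.2.2.2, 14.2.2.2.1.1 to .3, 14.2.2.2.2.1 to .2 = 6.
- Model-based comparisons: 12 tables × 4 visits = 48. Of these, 10 subgroup tables × 4 = 40 and 2 main tables × 4 = 8. One of the eight is the key secondary comparison.
- LS-mean figures: 14.2.2.1, 14.2.2.1.1 and 14.2.2.1.2 = 3.
- Unaffected: the descriptive parts of the 12 tables and the bar charts in Figures 14.2.2.2, 14.2.2.2.1 and 14.2.2.2.2.

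The SAP contains patterns for the repair. Section 4.10.8 drops the term for TSQM-9, and the WOMAC A responder model in 4.10.1.3 uses only study site and Baseline WOMAC A score.

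**The case against.** The best defence is that a covariate missing for everyone has one practical remedy, to leave it out, and that 4.10.8 already shows it. Section 4.10.2.1 asks only for a similar analysis, and the code in 4.10.1.1 is offered as a sample for WOMAC. Section 4.2.4 cannot be read with full rigour either: it assigns MMRM to the secondary endpoints generally, while responders get logistic regression and TSQM-9 gets ANCOVA. Part I is exploratory and has no multiplicity control.

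Much of this stands, and it keeps the consequence small. It does not remove the defect. Section 4.10.2.2 is specific to PGIC and names the covariate outright, and the authors thought the TSQM-9 case needed a written waiver.

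A reader might infer more than the documents support, in two respects.

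- *That the PGIC response is left undefined throughout.* Sections 2.4.2 and 4.10.2.1 both name the PGIC score, and 4.2.6 lists PGIC separately from WOMAC change from Baseline. What conflicts is the WOMAC sample code, the three figure titles, and the last bullet of 2.4.2.1, which can be read either way. That calls for tidying; the endpoint itself is defined.
- *That Part II would lose all its PGIC records.* Protocol 9.2.4 does list the endpoint's Baseline score as a covariate, and 9.4.3 has key secondary endpoints assessed like the primary, whose model contains Baseline score. But protocol 9.4 leaves the full details to a separate Part II SAP, which is not among the documents, and 9.4.3 compares categorical endpoints by chi-square or exact tests with no covariate. No count of lost Part II records can be given.

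**Conclusion.** The point holds as a rule that cannot be run as written. Read literally, the SAP yields no model-based PGIC result in Part I, including the key secondary comparison at Week 12. The conclusion rests on the collection schedule and the covariate text; it does not depend on enrolment or dropout.

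Its weight is moderate. No estimate is biased, since the model either fails or is run without the term. Descriptive results stand, and the key secondary label carries no confirmatory weight in Part I. It should still be corrected, because PGIC is second in the sequential test of key secondary endpoints that protocol 9.4.3 sets out, and its Part II model should be fixed in advance.

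Removing the term makes the records usable. It does not guarantee that every model can be estimated, because study site remains a covariate and the documents do not give the number of Part I sites.

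**What to change.** - SAP 4.2.4: add that the Baseline score of the endpoint is omitted for PGIC and TSQM-9, which have no Baseline assessment.
- SAP 4.10.2.1: state that the response is the observed PGIC score at each visit, with treatment, week, treatment-by-week interaction, Baseline WOMAC A score and study site, and that the `chg` response in the 4.10.1.1 code does not apply.
- SAP 4.10.2.2: list Baseline WOMAC A score and study site only, as in 4.10.1.3. Name subscale A, since the present text says only WOMAC.
- SAP 7.1: retitle Figures 14.2.2.1, 14.2.2.1.1 and 14.2.2.1.2 as LS mean PGIC score.
- SAP 2.4.2.1, last bullet: reword so that change from Baseline applies to the WOMAC subscales and not to PGIC.
- Part II SAP: carry the same exception, because protocol 9.2.4 has the same general covariate rule.

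The cost is wording, two model statements (MMRM and logistic) and three figure titles. It needs no new data and does not affect sample size or type I error.

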#### **4.2.5. Multiple Comparisons/Multiplicity**

As all analyses of the Part I data are exploratory in nature, there will be no controls for multiplicity.

#### **4.2.6. Subpopulations**

The analyses of WOMAC A, B and C change from Baseline and PGIC will be carried out for the subgroup of patients with WOMAC A (pain) average of Screening 2 and Day 1 scores of 5 to <6, 6 to <7, and ≥7 to 9, in order to assess any differences in treatment response in those groups, which were used as a stratification factor in randomization. These analyses will also be presented by unilateral/bilateral hip OA.

Other preplanned subgroups analyses (per aspiration status, Kellgren-Lawrence (K-L) grade, gender and the baseline pain score, etc.) will not be performed for Part I data. Other subgroups may be defined and explored after all pre-planned analyses have been completed to further elucidate study results.

---

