## 5. CHANGES TO PLANNED ANALYSES

There are no major changes to the planned analyses.

The following minor changes were made:

1. As a result of the six patients who were unable to receive complete study drug administration, the analysis populations were updated as follows:
  - a. The FAS was updated to clarify that this includes only patients who received a full dose of study drug ([Section 3.1](#)).
  - b. The SP was updated to clarify that this includes all patients who received at least one dose (full or partial) of study drug ([Section 3.1](#)).
2. Study site was added as a covariate, since it was determined in previous studies to be an important covariate ([Section 4.2.4](#)).
3. The protocol indicates that categorical end points will be compared via chi-square or exact tests. Instead, logistic regression will be used to analyze the WOMAC A pain ([Section 4.10.1.3](#)), PGIC categorical ([Section 4.10.2.2](#)) and OMERACT responder ([Section 4.10.3](#)) outcomes. This allows us to control for covariates in the models.

---

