## 7. CLINICAL STUDY REPORT APPENDICES

### 7.1. Statistical Tables and Figures to be Generated

Table 14.1.1	Patient Enrollment and Disposition
Table 14.1.2	Demographic and Baseline Characteristics (Safety Population)
Table 14.1.3	Osteoarthritis History and Index Hip Characteristics (Safety Population)
Table 14.1.4	Summary of Major Protocol Deviations (Safety Population)
Table 14.1.5	Study Drug Exposure Summary (Safety Population)
Table 14.2.1.1	Analysis of WOMAC A Pain Subscale (Full Analysis Set)
Figure 14.2.1.1	LS Mean Change from Baseline (+/- SE) in WOMAC A Pain Subscale Over Time (Full Analysis Set)
Table 14.2.1.1.1	Analysis of WOMAC A Pain Subscale, Patients with Baseline WOMAC A Pain Score 5 to <6 (Full Analysis Set)
Table 14.2.1.1.2	Analysis of WOMAC A Pain Subscale, Patients with Baseline WOMAC A Pain Score 6 to <7 (Full Analysis Set)
Table 14.2.1.1.3	Analysis of WOMAC A Pain Subscale, Patients with Baseline WOMAC A Pain Score $\geq 7$ to 9 (Full Analysis Set)
Figure 14.2.1.1.1	LS Mean Change from Baseline (+/- SE) in WOMAC A Pain Subscale Over Time by Baseline WOMAC A Pain Score (Full Analysis Set)
Table 14.2.1.1.2.1	Analysis of WOMAC A Pain Subscale, Patients with Unilateral Hip OA (Full Analysis Set)
Table 14.2.1.1.2.2	Analysis of WOMAC A Pain Subscale, Patients with Bilateral Hip OA (Full Analysis Set)
Figure 14.2.1.1.2	LS Mean Change from Baseline (+/- SE) in WOMAC A Pain Subscale Over Time by Unilateral/Bilateral Hip OA (Full Analysis Set)
Table 14.2.1.2	Analysis of WOMAC B Stiffness Subscale (Full Analysis Set)
Figure 14.2.1.2	LS Mean Change from Baseline (+/- SE) in WOMAC B Stiffness Subscale Over Time (Full Analysis Set)
Table 14.2.1.2.1.1	Analysis of WOMAC B Stiffness Subscale, Patients with Baseline WOMAC A Pain Score 5 to <6 (Full Analysis Set)

---

Table 14.2.1.2.1.2	Analysis of WOMAC B Stiffness Subscale, Patients with Baseline WOMAC A Pain Score 6 to <7 (Full Analysis Set)
Table 14.2.1.2.1.3	Analysis of WOMAC B Stiffness Subscale, Patients with Baseline WOMAC A Pain Score $\geq 7$ to 9 (Full Analysis Set)
Figure 14.2.1.2.1	LS Mean Change from Baseline (+/- SE) in WOMAC B Stiffness Subscale Over Time by Baseline WOMAC A Pain Score (Full Analysis Set)
Table 14.2.1.2.2.1	Analysis of WOMAC B Stiffness Subscale, Patients with Unilateral Hip OA (Full Analysis Set)
Table 14.2.1.2.2.2	Analysis of WOMAC B Stiffness Subscale, Patients with Bilateral Hip OA (Full Analysis Set)

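### The SAP aims to assess differences in treatment response between the baseline-pain strata but plans only an analysis inside each stratum, with no between-stratum estimate

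*SAP*

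**What the plan says.** SAP 4.2.6 sets the method: "The analyses of WOMAC A, B and C change from Baseline and PGIC will be carried out for the subgroup of patients" in each of three bands of the average Screening 2 and Day 1 WOMAC A score. It gives the purpose as "in order to assess any differences in treatment response in those groups". A further sentence covers laterality: "These analyses will also be presented by unilateral/bilateral hip OA".

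The repeated-measures model is given in SAP 4.10.1.1 as "model chg = base armcd avisitn armcd*avisitn site base_womaca". It contains a treatment-by-week term. Baseline WOMAC A enters only as a main effect, and there is no stratum or treatment-by-stratum term. The section asks for LS mean differences from placebo with 95% CIs and two-sided p-values.

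SAP 7.1 lists a separate table for each stratum, for example "Analysis of WOMAC A Pain Subscale, Patients with Baseline WOMAC A Pain Score 5 to <6 (Full Analysis Set", and separate tables for unilateral and bilateral disease. With five subgroups and five outcomes (WOMAC A, B, C, continuous PGIC, categorical PGIC) that makes 25 tables, plus figures that show the subgroups together. Categorical PGIC is analysed by logistic regression at each visit (SAP 4.10.2.2).

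The SAP does not use the phrase separate models. That reading follows from 4.2.6, the model code and the table list taken together.

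**The concern.** Whether response differs between strata is a question about the difference between treatment effects. The plan produces the effects one stratum at a time and never estimates that difference or its standard error. A reader is left to compare three estimates and three p-values by eye. In strata this small, a significant result next to a non-significant one is common even when the drug works equally well in both.

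The exploratory label in SAP 2.4 and 4.2.5 lowers the stakes but does not close the gap between aim and method. Protocol 9.1 and 9.4 allow Part I results to inform how Part II is run, and SAP 1.2 foresees use in filings and manuscripts.

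**Working it through.** **Inputs.** Difference 0.65, SD 2.0, two-sided alpha 0.05 and 6% dropout, from SAP 4.1 (stated there for Part II). Part I size about 70, or 35 per arm (SAP 4.1). The SAP's FAS requires a full dose and six patients did not receive one (SAP 3.1 and 5), so it may hold about 64. Stratum sizes are not given; equal thirds are assumed.

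**1. The plan's own figures.** With n = 2·SD²·(1.960 + 1.2816)² / d²:
- Primary: 2 × 4.0 × 10.507 / 0.4225 = 198.9, so 199; 199 / 0.94 = 211.7, so 212. This matches.
- First key secondary: 2 × 4.516 × 10.507 / 0.4624 = 205.2, so 206; 206 / 0.94 = 219.1, so 220. This matches.

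No size, power or error rate is stated for the stratum comparison.

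**2. Patients per arm per stratum.** 70 / 6 = 11.7 and 64 / 6 = 10.7, so roughly 10 to 12.

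**3. Power in one stratum and chance of a mixed verdict.** Power p comes from the noncentral t with 2n − 2 df and noncentrality 0.65 / (2.0·√(2/n)). With the same true effect in all strata, the chance that some but not all are significant is 1 − p³ − (1 − p)³.

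| n per arm | p at 0.65 | mixed verdict |
|---|---|---|
| 10 | 10.6% | 28% |
| 11 | 11.2% | 30% |
| 11.7 | 11.7% | 31% |

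With no effect anywhere, p = 0.05 and the chance is 1 − 0.000125 − 0.857 = 14%.

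**4. Sensitivity (N = 70).** For common effects of 1.0, 1.5 and 2.0 the mixed-verdict chance is 50%, 73% and 70%. Strata split 25/35/40 or 20/30/50 leave it at 31% for 0.65. These figures cover one endpoint at one visit and ignore covariate adjustment.

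**5. Estimates compared by eye (N = 70).** The SE of one stratum's effect is 2.0·√(2/11.67) = 0.83, with a 95% CI of about ±1.6. With a common effect of 0.65, one estimate points the wrong way with probability Φ(−0.65/0.828) = 0.216, so at least one of three does with probability 1 − 0.784³ = 52%. The average gap between the largest and smallest estimate (simulated) is 1.4 points, about twice the effect.

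**6. A direct contrast.** Simulation with 12 per arm per stratum (20,000 runs) compared a treatment-by-stratum F test with reading the strata by significance, when no difference exists:

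| common effect | F test rejects | mixed verdict |
|---|---|---|
| 0 | 5.3% | 14% |
| 0.65 | 5.0% | 31% |
| 1.5 | 4.9% | 73% |

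**7. Precision of that contrast.** Between two strata the SE is 0.828 × √2 = 1.17. A gap of (1.960 + 0.842) × 1.17 = 3.3 points is needed for 80% power. At N = 64 the SE is 1.22 and the gap 3.4.

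**The case against.** **No significance rule is written.** A reader might infer that the SAP compares strata by which p-values fall below 0.05, or that the planned output cannot test a difference at all. Neither is supported. The SAP sets no such rule, it plans within-stratum estimates with CIs, and the figures show the strata together. The strata are independent, so a reader could derive a contrast and its SE by hand. This stands: the accurate statement is that no contrast is specified.

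**Part II selection.** A reader might infer that a false contrast would lead to enriching Part II by pain stratum. Neither document proposes that. The specific use named for Part I is to check the sample-size assumptions and whether fewer than 440 patients would do.

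**Laterality.** The aim of assessing differences is attached to the pain strata; laterality results are only to be presented. Outcomes in unilateral patients at Weeks 1, 4, 8 and 12 are a listed secondary endpoint (Protocol 9.2.3.3, SAP 2.4.2.1), so analysing that group alone is what the protocol asks for. This stands.

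**Ambiguous wording.** The sentence speaks of differences in the groups, which could mean drug against placebo within each. That is possible, but if it is the intent the SAP should say so and call the results descriptive.

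**The replacement is weak too.** This is true: a gap of 3.3 points is about five times the planned effect. But an interval that wide shows how little can be concluded, whereas three separate p-values hide it.

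**Model size.** If all seven visits from Week 1 to Week 24 enter, one model has 2 × 3 × 7 = 42 cell means plus site effects. Three separate models fit the same 3 × 14 = 42, with three sets of site effects and three unstructured matrices of 28 parameters instead of one. The SAP does provide for non-convergence.

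**Conclusion.** The point holds for the three baseline-pain strata. The SAP states a between-stratum aim and plans only within-stratum analyses. At the plan's 0.65 and SD 2.0, with equal strata of 10 to 12 per arm, each stratum has about 11–12% power. Significance would disagree across strata in about 28–31% of trials with an identical true effect, and in 14% with none. The rate depends on the true effect and is higher for common effects of 1.0 to 2.0.

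The point does not extend to a claim that differences are untestable, to any planned selection for Part II, or to the unilateral-OA analyses as such. Because Part I is exploratory, this is a worthwhile and inexpensive correction and does not threaten the primary analysis.

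**What to change.** - **WOMAC A, B, C and continuous PGIC:** fit one MMRM on the full FAS, adding the randomization stratum, stratum × week, treatment × stratum and treatment × stratum × week. From that model report the treatment difference in each stratum and the Week 12 between-stratum differences, all with 95% CIs.
- **Categorical PGIC:** add stratum and treatment × stratum to the logistic model at each visit where the data allow it to be fitted.
- **Labelling:** mark per-stratum p-values as descriptive.
- **Precision:** state in 4.2.6 that at about 70 patients the SE between two strata is about 1.2 points, that about 3.3 points would be needed for 80% power, and that large differences cannot be excluded.
- **Laterality:** keep the unilateral-OA treatment comparisons at Weeks 1, 4, 8 and 12. Add a treatment × laterality estimate with its CI only if unilateral and bilateral results are to be compared.

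The cost is SAP wording and a change of model code; no new data are needed. The downside is a covariance matrix assumed common to the strata and more fixed effects in a single model.
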